4.1.6. Other variables

In the data collection form, the baseline characteristics of the research participants will be measured, including sociodemographic variables, comorbidities and the “NEWS-2 score” that will be adjusted for secondary analyzes if they are associated with the outcomes.

4.2. Selection of the Study Population

4.2.1 Inclusion criteria:

- Adult subjects over 18 years of age.
- SARS CoV2 / COVID 19 disease confirmed by antigen detection tests authorized by INVIMA or by RT-PCR in any of the laboratories that report to the Departmental Health Secretary, approved for the diagnosis of COVID-19 by the National Institute of Health.
- Onset of SARS CoV2 / COVID 19 illness 7 days ago or less.
- Subjects with mild disease.
- Informed consent signature.

4.2.2 Exclusion criteria:

- Medical history of liver disease.
- History of allergy to ivermectin or any of its components.
- Belonging to another clinical trial that evaluates the efficacy of an investigational drug against COVID-19. The use of other treatments outside of clinical trials is allowed.
- Severe pneumonia at the time of randomization.
- Pregnant or nursing women.
- Subjects receiving Warfarin, erdafitinib, or quinidine.
- Subjects who have received the D11AX22 molecule (ivermectin) within 5 days prior to randomization.
- Inability to evaluate recent liver enzymes, no more than 3 days prior to selection.
- Elevation in basal liver enzymes > 1.5 times the normal level.
- Subject whose contact with study personnel occurs between days 5-7 and at that time manifests significant and progressive improvement \geq 48 hours in signs and symptoms of COVID-19.

4.2.3 **Early withdrawal from the study:**

Subjects will be withdrawn from the study:

1. In the event that the investigation product is discontinued within 24 hours of randomization.

4.2.4 Randomization:

Central 1: 1 randomization in blocks of 4 will be generated by a list of random numbers, a separate staff of the telephone allocation system will assign treatment to each of the research participants on a first-come, first-served basis.

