4.1.5. Outcomes

4.1.5.1. Primary outcome to be evaluated

To determine the time until the resolution of the symptoms in the two study groups.

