4.1.5.3. Definitions

SARS-CoV-2/COVID-19 Mild illness : Outpatient, or inpatient with supplemental oxygen NOT NEEDING high-flow nasal oxygen, non-invasive mechanical ventilation, or mechanical ventilation.

Severe pneumonia due to SARS-CoV-2/COVID-19 : Inpatient with high-flow nasal cannula oxygen, non-invasive mechanical ventilation or needing mechanical ventilation or ECMO

7-point Clinical Scale:

This scale has been used in clinical studies in subjects with COVID-19 and influenza.^{43,44} The seven-point clinical scale has the following categories:

1. Non-hospitalized subject, able to perform daily activities
2. Non-hospitalized subject, unable to perform daily activities
3. Hospitalized, no need for supplemental oxygen
4. Hospitalized, in need of supplemental oxygen
5. Hospitalized, in need of high-flow nasal oxygen or non-invasive mechanical ventilation
6. Hospitalized, in need of mechanical ventilation or ECMO
7. Death

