4.1. Primary outcome

-Time until the resolution of the symptoms in the two study groups. Number of days from randomization visit to the first symptom-free day (score of 0 on the 8-point scale). Variable measured during the 21 days of follow-up.

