6.1. Primary outcome

The main analysis will be the survival analysis for the primary outcome variable (time to disappearance of symptoms associated with COVID-19), using the log-rank test to compare ivermectin versus placebo as a control group. Symptom resolution will be assessed using the 8-point ordinal scale, which has the following categories: (0) -Patient without symptoms, (1) -Non-hospitalized patient, with the ability to do daily activities, (2) -Non-hospitalized patient, unable to do daily activities, or using oxygen at home (3) -Hospitalized, without need for supplemental oxygen, (4) -Hospitalized, with need for supplemental oxygen, (5) -Hospitalized, with need for high-flow nasal oxygen or non-invasive mechanical ventilation, (6) -Hospitalized, in need of mechanical ventilation or ECMO, (7) -Death.

The outcome variable will be the time to recovery, defined as the first day, during the 21 days of follow-up, in which the patient reports a score of (0) on the 8-point scale.

Patients who do not report recovery from symptoms and those who die during study follow-up will be considered as censor data on day 21 or until death. Kaplan-Meier estimator will be used to report the recovery percentage throughout the follow-up and at day 21. Relevant treatment efficacy parameter is the recovery rate ratio (RR) with its respective 95% confidence interval (CI), which will be estimated by Cox proportional-hazard model. Given that the primary outcome may take two values; equal to 1 when the patient reports recovery of symptoms and 0 when not, a $RR > 1$ will indicate a favorable result for ivermectin compared to placebo.

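### The primary outcome is time to symptom resolution, but no criterion requires a symptom at randomisation, so patients whose outcome is already fixed can enter the primary analysis

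*Supplement*

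**What the plan says.** **Endpoint.** Protocol 4.1.5.1 sets the primary outcome: "To determine the time until the resolution of the symptoms in the two study groups". SAP 4.1 counts days from the randomisation visit to the first day at score 0. SAP 6.1 gives the event as "defined as the first day, during the 21 days of follow-up, in which the patient reports a score of (0) on the 8-point scale". Neither places a condition on the score at randomisation.

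**Eligibility.** Protocol 4.2.1 requires adult age, a positive antigen test or RT-PCR, consent, "Onset of SARS CoV2 / COVID 19 illness 7 days ago or less" and "Subjects with mild disease". Protocol 4.1.5.3 defines mild illness by care setting and respiratory support alone: "Outpatient, or inpatient with supplemental oxygen NOT NEEDING high-flow nasal oxygen" and no ventilation. Any outpatient therefore meets it. The one related exclusion, in 4.2.2, is "Subject whose contact with study personnel occurs between days 5-7 and at that time manifests significant and progressive improvement", and that improvement must have lasted at least 48 hours.

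**Scale.** The protocol's scale (4.1.5.3, rated from D1 in the 4.3.3 table) has seven points and starts at 1, an outpatient able to carry on daily activities. Only the SAP has score 0.

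**Analysis set.** SAP 5.1 takes all randomised patients as the primary population. Neither SAP 6.1 nor SAP 6.5 says how a patient at score 0 at randomisation is analysed.

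**The concern.** The eligibility rules suit a trial of deterioration. A patient who has just become symptom-free can still deteriorate, but cannot resolve a second time. The amendment log gives low risk of deterioration as the reason for the day 5 to 7 exclusion, which was the earlier endpoint. The log lists no eligibility change when resolution became primary.

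The exclusion misses three groups:

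- patients contacted before day 5;
- patients whose improvement has lasted less than 48 hours;
- patients whose symptoms resolve between contact and randomisation.

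For any of them already at score 0, treatment cannot change the outcome. They could be counted as events at time zero, as events at the first follow-up call, or left out, and the plan does not say which. The first two add events unrelated to treatment and pull the rate ratio toward 1. The third leaves fewer informative events than planned. What is at stake is some power and a clear reading of the estimate.

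**Working it through.** **Inputs (protocol 4.4, SAP 2.2).** Hazard ratio 1.4, alpha 0.05 (taken as two-sided, since sidedness is not stated), power 80%, 390 subjects, 75% resolved by day 21, 290 events, 1:1 allocation, 2% loss, 76 excluded, total 476. The share *f* at score 0 at randomisation is not in the documents, so an assumed range of 0 to 20% is shown.

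**The plan's own figures.**

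- Schoenfeld: 4 × (1.960 + 0.842)² / (ln 1.4)² = 278 events. Freedman: 283. The plan has 290.
- Power at *d* events = Φ(√d × ln(1.4)/2 − 1.960). At 290: 17.03 × 0.3365/2 − 1.960 = 0.905, so power is 0.817.
- 390 × 0.75 = 292.5 events. 390/0.98 = 398, and 398 + 76 = 474 against 476 stated.

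The stated design reproduces, with about two points of power to spare.

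**Effect of patients at score 0.** Three readings:

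- A: they leave the risk set, so events = 390 × (1 − f) × 0.75.
- B: the planned 290 events already count them, so informative events = 290 − 390f. This is possible because the 75% rests partly on data from this study.
- C: they are kept as events at day 0. This was a log-rank simulation with 2,000 runs, 195 per arm, exponential times in whole days and 75% resolved by day 21.

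| f (assumed) | A: events | A: power | B: events | B: power | C: power | C: approximate HR |
|---|---|---|---|---|---|---|
| 0% | 292.5 | 0.82 | 290 | 0.82 | 0.82 | 1.42 |
| 5% | 277.9 | 0.80 | 270.5 | 0.79 | 0.78 | 1.39 |
| 10% | 263.2 | 0.78 | 251 | 0.76 | 0.71 | 1.35 |
| 20% | 234 | 0.73 | 212 | 0.69 | 0.63 | 1.31 |

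The simulated powers carry a standard error of about 0.01. The same runs with these patients dropped gave 0.82, 0.81, 0.76 and 0.74, so simulation and formula A agree to within about two points.

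**The case against.** The strongest reply is that few patients are exposed.

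- Onset of illness means that the patient had symptoms at some time, so a reader might infer that people who never had symptoms can enter, but the criteria do not support that.
- The amendment log says that RT-PCR results usually come after 5 days, which puts many contacts inside the window of the improvement exclusion.
- Eligibility is checked at both the screening and the randomisation visit (protocol 4.3.2 and 4.3.3), and the log says that the two visits can fall on one day.

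All of this stands, and it narrows the gap. It does not close it, because the second check tests the same criteria and none of them asks for a symptom.

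A reader might also infer that power certainly falls below 80%. One route takes a constant hazard of −ln(0.25)/20 = 0.0693 per day and a one-day wait, so 1 − exp(−0.0693) = 6.7% are already recovered. It then takes 27 of 400 patients off the 290 events, leaving 263 and power 0.78. The documents do not support this. The wait may be zero, and constant hazard probably overstates early recovery. Under that model, patients who recover before randomisation were never among the later events. The same 6.7% gives 390 × 0.933 × 0.75 = 273 events and power of about 0.79.

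Nor do the documents support false-positive bias. Randomisation balances such patients in expectation, so the pull is toward no effect.

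Finally, leaving them out departs from the all-randomised population in SAP 5.1, in a trial that already excludes 76 patients. That is fair, and it is why the analysis that includes them should be reported as well.

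**Conclusion.** The gap is real and minor. As written, the plan can randomise a patient whose primary outcome was settled before treatment and keep that patient in the primary population, with no rule for the event time. If such patients leave the risk set, the loss is about two points of power at 5% and four at 10%. It is larger if they are kept as day-0 events: about 0.78 and 0.71 in the simulation. These sizes rest on an assumed share, a two-sided alpha and the plan's own hazard ratio and event rate. The true share may be near zero where screening and randomisation coincide. The mismatch between eligibility and endpoint, and the missing handling rule, do not depend on the share.

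**What to change.** 1. **Protocol 4.2.1:** add that at least one COVID-19 symptom (score 1 or more on the SAP's 8-point scale) is present at the randomisation visit. Protocol 4.3.2 lists the collection of clinical data after randomisation, so place this check with the eligibility verification, before allocation.
2. **Protocol 4.1.5.3 and 4.3.3:** replace the 7-point scale with the 8-point scale, so that score 0 can be recorded at D1. The SAP already presumes an enrolment score on the 8-point scale (4.2 and 6.3).
3. **SAP 5.1 and 6.1, before unblinding:** for patients already randomised, leave those with a pre-treatment score of 0 out of the time-to-resolution analysis in both arms. Report their number by arm and keep them in the secondary and safety analyses. Give the analysis that includes them as a sensitivity analysis, with one stated rule for their event time. If only the 7-point scale was recorded at D1, write down beforehand how score 0 is derived from that visit's clinical data.

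The cost is a short amendment to the criteria, the scale and the order of procedures, marginally slower recruitment, and a small departure from the all-randomised set. Because the exclusion uses a pre-treatment score and applies alike to both arms, it preserves the randomised comparison. Without the criterion, keeping 390 symptomatic patients would take 390/0.95 = 411 at an assumed 5%, or 390/0.90 = 434 at 10%, before the 2% loss and the 76 exclusions.

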4.2. Selection of the Study Population

4.2.1 Inclusion criteria:

- Adult subjects over 18 years of age.
- SARS CoV2 / COVID 19 disease confirmed by RT-PCR in any of the laboratories that report to the Departmental Health Secretary, approved for the diagnosis of COVID-19 by the National Institute of Health.
- Onset of SARS CoV2 / COVID 19 illness 5 days ago or less.

- Subjects with mild disease.
- Informed consent signature.

4.2.2 Exclusion criteria:

- Medical history of liver disease.
- History of allergy to ivermectin or any of its components.
- Belonging to another clinical trial that evaluates the efficacy of an investigational drug against COVID-19. The use of other treatments outside of clinical trials is allowed.
- Severe pneumonia at the time of randomization.
- Pregnant or nursing women.
- Subjects receiving Warfarin, erdafitinib, or quinidine.
- Subjects who have received the D11AX22 molecule (ivermectin) within 5 days prior to randomization.
- Inability to evaluate recent liver enzymes
- Elevation in basal liver enzymes > 1.25 times the normal level.

4.2.3 Early withdrawal from the study:

Subjects will be withdrawn from the study:

1. In the event that the investigation product is discontinued within 24 hours of randomization.

4.2.4 Randomization:

Central 1: 1 randomization in blocks of 4 will be generated by a list of random numbers, a separate staff of the telephone allocation system will assign treatment to each of the research participants on a first-come, first-served basis.

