2. PROBLEM STATEMENT AND JUSTIFICATION

Valle del Cauca is the department with the second highest number of cases and lethality in Colombia. As of April 26, 2020, we have 841 cases, of which 12% have required hospitalization and 8.7% require intensive care, with a fatality rate of 6.5%.¹⁰ Every day a greater number of cases are reported in Valle del Cauca.

In the early or mild phases of the infection, the currently recommended procedure is symptom control, with no medication proven to reduce disease progression.¹¹ However, about 20% of subjects progress to severe disease, so it is urgent to identify interventions that mitigate this progression. This is especially important considering that, as with other antiviral medications, early reduction in viral load during mild forms of the disease has favorable effects on its outcome.¹²

The D11AX22 molecule (ivermectin) is a new therapeutic proposal against COVID-19. The D11AX22 molecule (ivermectin) is one of the most important drugs ever discovered and has been recognized as a benchmark by the American Chemical Society. Its discoverers were awarded the Nobel Prize in 2015 for demonstrating its great efficacy as a broad-spectrum antiparasitic.¹³ Originally introduced as an antiparasitic in veterinary medicine in the early 1980s, it is a drug that eliminates a wide range of endo and ectoparasites in livestock and other animals. For more than 35 years it has been used in humans with great efficacy and safety to treat endoparasites that are difficult to control, such as filariasis, onchocerciasis or strongyloidiasis, also ectoparasites, such as pediculosis capitis and myiasis.¹⁴⁻¹⁶

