Another possible mechanism of action would be by enhancing the immune system as has been described for onchocerciasis and psoriasis in humans.²⁹⁻³³

The half-life of the D11AX22 (Ivermectin) molecule in plasma is at least 16 hours. It is absorbed mainly in the intestine and passes into the bloodstream after being administered orally, reaching a therapeutic peak 4 hours after oral administration. It is metabolized in the liver and its metabolites are almost exclusively excreted in the feces, less than 1% of the dose is excreted in the urine.¹⁴ The recommended therapeutic doses as antiparasitic vary between 0.05 and 0.40 mg/kg without undesirable effects or risk to human life; When administered in doses of 0.20 mg/kg, the maximum plasma concentrations reached after four hours are 20 ng/ml, while toxic doses are on the order of 6.6 to 8.6 mg/kg, which can lead to vomiting, blurred vision, mydriasis, ataxia, tremor, and coma. Lethal doses are on the order of 24 mg/kg. No contraindications for its use in humans or negative effects on reproduction or pregnancy have been described, and at least 250 million people in the world have received different doses of this molecule. All of the above allows us to consider the D11AX22 (Ivermectin) molecule as a very safe drug in humans, in whom low toxicity has been seen, unlike other animal species.³⁴

Thus, taking into account the in vitro inhibitory capacity against different types of viruses, including SARS CoV2, the encouraging clinical data in humans with COVID 19, the extensive experience in humans that has demonstrated safety using this drug for other pathologies, and the extensive use of the molecule D11AX22 (ivermectin) by this group of investigators,³⁵⁻³⁹ There is sufficient rationale to evaluate its use in adults with mild COVID-19 illness.

Given the high morbidity that this disease generates, and the urgent need to find strategies that allow us to reduce disruption in our current lifestyle through safe measures, we propose a double-blind, randomized, placebo-controlled clinical trial to evaluate the efficacy of the D11AX22 (ivermectin) molecule in adults with mild COVID-19 disease.

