4.4 Sample size

According to the literature and previous data in this study, 75% of the subjects will have the event of interest (disappearance of symptoms) by day 21. Thus, including 390 subjects, we will identify 290 events of interest. With this sample size we will have a power of 80% and an Alpha of 0.05 to detect a Hazard ratio of 1.4 of ivermectin vs. placebo in time to symptom resolution. Taking into account a 2 % follow-up loss and 76 subjects who will be excluded from the primary analysis¹, we will include a total of 476 subjects in the study.

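### The 5-day ivermectin look-back does not cover the 7-day onset window, so patients treated at the start of this illness can be randomised: a small loss of contrast, not a bias

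*Supplement*

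**What the plan says.** The eligibility rules in section 4.2 of the current protocol contain four statements that bear on this.

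- Onset window (4.2.1): "Onset of SARS CoV2 / COVID 19 illness 7 days ago or less".
- Prior ivermectin (4.2.2, an exclusion): "Subjects who have received the D11AX22 molecule (ivermectin) within 5 days prior to randomization".
- Other treatment (4.2.2): "The use of other treatments outside of clinical trials is allowed".
- Improving patients (4.2.2): someone contacted on days 5-7 who "at that time manifests significant and progressive improvement" lasting 48 hours or more is excluded.

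The superseded protocol had "Onset of SARS CoV2 / COVID 19 illness 5 days ago or less" with the same 5-day look-back, so the two windows were then equal. The entry for Amendment 2 in the summary of changes widens the onset window because test results were hard to obtain within 5 days. It does not mention the ivermectin look-back.

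The latest SAP (version of 20 September 2020) does not take up prior ivermectin. Section 6.3 names enrolment score, symptom duration, comorbidities, age and sex as possible effect modifiers, to be examined only if differences are found. Its one sensitivity analysis is per protocol, a population defined in section 5.1 by adherence and complete data.

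**The concern.** With equal windows, the look-back covered the whole illness, so nobody could enter having already taken the test drug for it. In the current text it no longer does for patients randomised more than 5 days after onset.

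The protocol's case for the trial (section 2) is that "early reduction in viral load during mild forms of the disease has favorable effects on its outcome". If that is right, a patient who took ivermectin in the first day or two may already have had some of its benefit. In the placebo arm that patient is not an ivermectin-free control. In the active arm the trial course may add less. Both pull the recovery rate ratio towards 1. At stake is a little power, together with some uncertainty about how much of a null result reflects dilution.

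**Working it through.** **1. The gap.** I take both windows to count back from randomisation; the visit table has eligibility checked at that visit.

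- Onset allowed: up to 7 days before.
- Ivermectin excluded: up to 5 days before.
- Uncovered: 7 − 5 = 2 days at most, roughly days 6 and 7 before randomisation, and only for patients randomised more than 5 days after onset.

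A daily course begun at onset escapes only if it stopped before it reached the 5-day window. For a patient randomised 7 days after onset, a dose taken 2 days after onset falls 5 days before randomisation and already excludes. Only very early and very short use gets through.

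**2. Is it plasma carry-over?** Section 2 says that the half-life of the "molecule in plasma is at least 16 hours". Five days is 120 hours, and 120/16 = 7.5 half-lives, leaving 0.5^7.5 ≈ 0.6%. Since 16 hours is a lower limit, more could remain: if the half-life were 24 or 36 hours (assumed values), 3.1% or 9.9%. At the stated figure carry-over is small. The issue is earlier treatment of the same illness.

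**3. The plan's own sample size.** Inputs from protocol section 4.4: "power of 80% and an Alpha of 0.05 to detect a Hazard ratio of 1.4 of ivermectin vs. placebo", 75% with the event by day 21, 390 subjects, 290 events, 2% loss, 76 excluded subjects, 476 in total. Allocation is 1:1. Sidedness is not stated; I assume two-sided.

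- Schoenfeld: 4 × (1.960 + 0.842)² / (ln 1.4)² = 277.3, so 278 events.
- Freedman: (1.960 + 0.842)² × (2.4/0.4)² = 282.6, so 283 events, within 3% of 290.
- Events: 390 × 0.75 = 292.5.
- Power at 290 events: √290/2 × ln 1.4 = 2.865; 2.865 − 1.960 = 0.905; Φ(0.905) = 81.7%.
- Total: 390/0.98 ≈ 398, and 398 + 76 = 474; rounding 398 up to 400 gives 476.

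The plan's figures reproduce.

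**4. Dilution.** The documents give no rate of prior ivermectin use, so f is assumed and shown as a range. Let f be the share of all randomised patients, in both arms, who slip through the gap and have no further treatment effect. Then approximately log HR = (1 − f) × ln 1.4, and power = Φ((1 − f) × 2.865 − 1.960).

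| f (assumed) | Patients among 390 | HR | Power at 290 events |
|---|---|---|---|
| 0% | 0 | 1.400 | 81.7% |
| 1% | about 4 | 1.395 | 81.0% |
| 2% | about 8 | 1.391 | 80.2% |
| 5% | about 20 | 1.377 | 77.7% |

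Power reaches 80% where (1 − f) × 2.865 = 2.802, that is f ≈ 2.2%.

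No further effect at all is the extreme case. If pre-treated patients kept half of the effect on the log scale, f = 2% would act like f = 1%, and power would be 81.0%.

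**The case against.** The other side has a good deal in its favour.

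- **The gap is narrow.** To pass through it, a patient must be randomised more than 5 days after onset, have taken ivermectin only in the first day or two, have taken none since, and not be improving. The share f is the product of these conditions, and nothing in the documents suggests that it is large. This stands.
- **The improvement exclusion removes some of these patients.** If early ivermectin works, those who benefited are the most likely to be improving on days 5-7. This stands in part: the criterion turns on improvement at contact, not on exposure, so pre-treated patients who are still unwell stay in.
- **A washout need not equal the onset window.** At the stated minimum half-life, 5 days is a workable washout, and other treatment outside trials is allowed anyway. That answers carry-over. It does not answer earlier treatment of the same illness with the test drug, and the amendment gives no reason for leaving the look-back as it was.

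A reader might also infer that pre-treated controls bias the comparison. They do not: prior use is fixed before randomisation and is balanced between arms in expectation. Nor do the documents support quoting a large loss. At f = 10% the same formula gives 73.2% power, but that needs one randomised patient in ten to pass every condition above and to have no further effect.

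**Conclusion.** The current eligibility text has a gap that neither the rest of the protocol nor the SAP closes. A patient randomised more than 5 days after onset, who took ivermectin only at the very start of this illness and has not been improving for 48 hours or more, can enter either arm.

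The consequence is a small loss of contrast. On the extreme assumption of no further effect, power stays at or above the planned 80% up to f of about 2.2%, roughly 9 of 390 patients (390 × 0.022 = 8.6), and is 77.7% at f = 5%. The true f cannot be derived from the documents. It would be going too far to say that this gap alone makes a null result uninterpretable. Minor priority, worth doing because it is cheap. The conclusion rests on the trial's own early-treatment premise, a two-sided test, and both windows counting back from randomisation.

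**What to change.** - **Eligibility.** Reconcile the two windows in section 4.2 so that, for remaining recruitment, the prior-ivermectin exclusion covers the whole current illness, from onset to randomisation.
- **Data.** Record ivermectin use since onset at screening. The protocol lists only general baseline, medical background and clinical data, so a specific item is needed.
- **Analysis.** In SAP section 6.3, pre-specify a repeat of the primary analysis without patients who took ivermectin between onset and randomisation. As this is a pre-randomisation characteristic, leaving them out keeps the randomised comparison intact.
- **Patients already randomised.** Do this only where the information exists or can be obtained from the participant or the records. Nothing in the documents shows that use beyond the 5-day look-back was collected, so report how many could not be classified.

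The cost is a short amendment, one added or reworded screening question, one sentence in the SAP, and a few more screen failures.
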